5.3 Treatment Assignment Procedures

5.3.1 Randomization Procedures

Subjects will be randomized in a 2:1 ratio to subject-collected DBS CMV monitoring with mobile technology support (n=100) or standard care with office-based testing (n=50). Additional subjects will be enrolled as retrospective observational controls and will not be randomized (n=450). The list of randomized treatment assignments will be prepared by statisticians at The Emmes Corporation (Emmes) and included in the enrollment module of Emmes' Internet Data Entry System (IDES). IDES will assign each subject a study arm from the list after demographic (date of birth, race/ethnicity, and sex) and eligibility data have been entered into the system. Randomization will be stratified by transplant site and subject's perceived ease of access to blood draw facility. Observational cohort will be enrolled in IDES after the required demographic and eligibility information are entered. Instructions for use of the enrollment module are included in the IDES User's Guide. Manual back-up randomization procedures are provided in the MOP for use in the event that the site temporarily loses access to the Internet or the online enrollment system is unavailable.

Subject IDs will be assigned to potential subjects, who have documented informed consent by signing an Informed Consent form, as they are screened. The subject ID will be used for all communications with outside institutions to ensure confidentiality.

Subjects who are randomized and drop out of the study prior to beginning follow-up (first scheduled test both arms) will be replaced. Over-enrollment is allowed to accommodate competitive enrollment and accommodate replacement subjects.

5.3.2 Masking Procedures

None

5.3.3 Reasons for Withdrawal

Any enrolled subject may withdraw or be withdrawn from the study for the following reasons:

- The subject (guardian) withdraws consent
- The study is terminated
- Subject fails to demonstrate proficiency in DBS sample collection

- For any reasons that, in the opinion of the investigator, precludes the subject's participation in the study
- Subject has been enrolled inappropriately based on inclusion/exclusion criteria; these subjects may be replaced, or
- Initiation of end of life care
- If the subject has morphological relapse prior to the start of study related CMV surveillance testing.

Subjects may withdraw from participation in the study at any time. If a subject withdraws or is withdrawn prior to completion of the study, the reason for this decision must be recorded in the case report forms (CRFs), although it is recognized that the subject can refuse to provide a reason. If a randomized subject is withdrawn prior to the first scheduled study test (or prior to the start of late CMV surveillance) for any reason, they will be replaced; however, they will not be moved over to the observational cohort.

For subjects who withdraw or are withdrawn prior to completion of the study, clinical information relevant to the secondary endpoint and the SAEs of special interest (proven/probable CMV disease) should continue to be obtained from the primary physicians' office or medical records until the end of the follow-up unless the subject withdraws consent .

The NIAID/DMID, the IRB and/or the FDA have the right to terminate this study at any time. Reasons for terminating the study may include, but are not limited to the following:

- Incidence of AE's indicating a potential health hazard
- Data recording is inaccurate or incomplete
- The Investigators has not been adhering to the protocol or applicable regulatory guidelines in conducting the study.

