not possible these supervised trainings may be completed remotely via video conferencing as an option (See MOP for details and instructions). The third session will be unsupervised with the subject performing the testing in their home or temporary residence nearby the transplant center This training session will be followed up with a phone call or in-person check-in and a questionnaire to assess understanding. At each session, the subject will have written instructions on performing the DBS testing and utilizing the web/mobile technology available for their reference. Each DBS training session requires the completion of a DBS collection. The study coordinator will be available to provide additional training session as needed. In addition, DBS collection instructional video is available on the study website. Prior to discharge from the transplant care team, study personnel must confirm that the subject demonstrates proficiency in DBS sample collection and use of the study website.

The mobile technology will consist of a notification system that sends weekly reminders by email and/or text message determined by the subject's preference to the subject to complete DBS self-collection procedures. The notifications are sent from a web-based, 21 CFR 11-compliant electronic data capture system created and maintained by The Emmes Company. The subject will log into the system on a computer or mobile device with internet access to set up study reminders and record sample collection and shipment information. The system will also house IRB-approved training materials and the web address of the United States Postal Services (USPS) so that shipments may be scheduled.

Subjects who are enrolled in the control arm of the randomized study will continue to receive their office-based CMV plasma testing as recommended by standard of care.

Quarterly follow-up contacts will be made with the primary care physicians of all randomized subjects enrolled in the study to obtain each subject's medical record. Data from each subject's medical record on immunosuppression, CMV disease status, any interim use of antiviral therapy for CMV disease or plasma reactivation, clinically recommended CMV test interval, any hospitalization record, relapse, and survival status will be collected.

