APPENDIX C: SCHEDULE OF EVENTS

			In	itial St	tudy Vi	sit ³						
Visit/Contact	Screening ¹	Enrollment ²	Training 1 ⁵	Training 2 ⁶	Training 3 ⁷	Discharge	DBS self- collection	Plasma Collection ⁴	Quarterly Contact 1	Quarterly Contact 2	Quarterly Contact 3	Final Study Visit
Days after HCT	60-180						60-365	60-365	90	180	270	365
Window (days)		N/2	4						±14	±14	±14	(+120)
Confirm informed consent		Х										
Eligibility assessment	X, Z											
Randomization		Х										
Review of medical history		X, Z										
Review of concomitant medication		X, Z				Х			Х	Х	Х	X, Z
Confirm CMV monitoring interval						Χ, Ζ			Х	Х	Х	
Adherence counseling ⁸			Х									
DBS collection and website training ⁹			Y	Y	Y		Y ¹⁰					
Provision of initial study kits						Y						

¹ It is recommended to have screening done approximately one month prior to planned discharge from the primary transplant clinic

² Screening, enrollment, and initial study visit (trainings for DBS arm) may occur on the same day as long as all trainings are completed by subjects with proficiency and confirmed by study personnel prior to discharge from primary transplant clinic.

³ Trainings 1-3 must be completed prior to planned discharge from the subject's primary transplant clinic.

⁴ Confirmatory plasma sample will be collected from DBS arm subjects if they had a CMV positive DBS.

⁵ Training with study staff supervision.

⁶ Training with study staff supervision.

⁷ Training without study staff supervision.

⁸ Adherence counseling should be done on all randomized subjects after enrollment but prior to discharge from primary transplant clinic.

⁹ DBS collection is required at each DBS training visit. Website and mobile technology training may be optional for training 2 and 3 as necessary.

¹⁰ DBS collection starts the week after discharge and ends approximately one-year post-HSCT

DMID Protocol Number 16-0098 CMV DBS Testing in HCT Recipients

Version 5.0 30 June 2022

			In	itial St	tudy Vi	isit ³						
Visit/Contact	Screening ¹	Enrollment ²	Training 1 ⁵	Training 2 ⁶	Training 3 ⁷	Discharge	DBS self- collection	Plasma Collection ⁴	Quarterly Contact 1	Quarterly Contact 2	Quarterly Contact 3	Final Study Visit
Days after HCT		60-180						60-365	90	180	270	365
Window (days)		N/A							±14	±14	±14	(+120)
Kit integrity monitoring ¹¹						Y	Y					
Subject questionnaire ¹²						Y	Y					Y
Provider questionnaire ¹³												Y
Safety monitoring									Х	Х	Х	Х

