Obtain interim medical records ¹⁴									Х	Х	Х	X, Z

X = performed for all randomized subjects

Y = performed for DBS arm subjects only

Z = performed for observational cohort only

GRAY columns may not be required. Depending on when a subject enrolls in the study, the duration of participation will be between 26 and 44 weeks. Columns marked in GRAY apply to those subjects whose participation includes these time points. If the scheduled quarterly visit is within 10 days of subject randomization, the corresponding quarterly visit will be waived.

¹¹ Subjects are instructed to report of any failures in DBS kits during the duration of study participation. At each time of subject reporting, study staff is responsible for uploading the reported information to Advantage eClinical eCRF. If reported problem meets adverse (AE) criteria, a separate AE form must be submitted.

[figure not shown]
¹² Patient questionnaire will be given after 3rd training session, 1 month after discharge, and at the end of study.

¹³ Primary care providers will be given a questionnaire at the time of last quarterly contact for medical records review.

¹⁴ Obtain CMV testing frequency and results, presence of CMV disease, use of antivirals of CMV treatment, and use of steroids for GVHD

[figure not shown]

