6.3. Analysis Populations

6.3.1. Intention-to-Treat Analysis (ITT) Population

The Intention-to-Treat population includes all participants in the randomized cohort in the intervention group to which they were randomly assigned, regardless of their monitoring compliance and regardless of subsequent withdrawal or deviation from the protocol. Participants who withdraw before discharge and participants that withdraw after discharge but before their first scheduled in-office CMV monitoring test will be considered as fail, which is not meeting the >90% threshold for the primary adherence analyses.

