6.5. Missing Data

6.5.1. Withdrawal Prior to First Recommended Monitoring Test

If participants withdraw prior to their first scheduled clinician-recommended CMV monitoring test, the number of recommended clinician-recommended CMV monitoring tests will be zero, monitoring compliance cannot be calculated. These participants will be included in the ITT analyses and considered as fail, not meeting the >90% threshold for the primary endpoint. They will not be included in the mITT or Completer analyses.

If the clinician recommended monitoring test interval is "No further monitoring required" at discharge and not changed until withdrawal or 1 year after HCT, then these participants will be included in the ITT analyses and considered as fail, not meeting the >90% threshold.

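### A proficiency check applied only in the DBS arm, after randomisation, can lead to withdrawal; such participants count as ITT failures and leave mITT and Completer, with no counterpart in the control arm

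*Protocol*

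**What the plan says.** **The check.** Protocol 4.1 provides three DBS training sessions and requires that, before discharge, "study personnel must confirm that the subject demonstrates proficiency in DBS sample collection and use of the study website". Appendix C puts the trainings after randomisation and before discharge ("Trainings 1-3 must be completed prior to planned discharge from the subject's primary transplant clinic") and codes them Y, where "Y = performed for DBS arm subjects only". Protocol 7.2.2 gives the control arm the same later activities apart from DBS collection, so it has no equivalent check.

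**The consequence.** Protocol 5.3.3 opens its list with "Any enrolled subject may withdraw or be withdrawn from the study for the following reasons" and includes "Subject fails to demonstrate proficiency in DBS sample collection". Protocol 5.3.1 adds: "Subjects who are randomized and drop out of the study prior to beginning follow-up (first scheduled test both arms) will be replaced". SAP 4.4.4 gives the replacement a fresh random allocation.

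**The scoring.** SAP 4.5.1 counts withdrawal before discharge as a failure. SAP 6.3.1 extends this to participants who "withdraw after discharge but before their first scheduled in-office CMV monitoring test will be considered as fail". SAP 6.5.1 keeps these participants in ITT as failures on the primary endpoint and says of the other populations: "They will not be included in the mITT or Completer analyses". Under SAP 6.3.3, Completer is a subset of mITT.

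**What is counted.** SAP 3.3.5 takes completed tests from the chart-review form. SAP 4.4.1 has both arms continue office monitoring at the clinician's interval.

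**The concern.** Take two randomised people with the same difficulty in collecting a finger-stick sample. In the control arm the difficulty is never tested. That person is followed to one year and scored on the office tests in the chart. In the DBS arm the person may be withdrawn before follow-up begins. The primary outcome is then a failure set by rule, and the person does not appear in mITT or Completer.

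This is removal after randomisation, in one arm only, for a reason that may be related to adherence. What is at stake is power and the size of the estimated benefit in the primary analysis, and whether mITT and Completer can be read as independent support for it. If non-proficient participants would have adhered somewhat, but less than others, the ITT and mITT estimates lie on opposite sides of the true DBS rate.

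**Working it through.** **Inputs from the documents.** 100 DBS and 50 control participants; success 0.80 in DBS and 0.50, 0.55 or 0.58 in control; two-sided 5% level (Protocol 11.2; SAP Table 2).

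**Assumed inputs, absent from the documents.** *f* is the share of the DBS arm withdrawn for non-proficiency. *q* is the proportion of those people who would have exceeded 90% on chart-recorded tests.

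**1. The plan's power.** Pooled normal approximation without continuity correction, power = Φ(z), z = (p₁ − p₂ − 1.96·s₀)/s₁. For 0.80 against 0.50, the pooled rate is 0.70, s₀ = √(0.70 × 0.30 × (1/100 + 1/50)) = 0.0794, s₁ = √(0.16/100 + 0.25/50) = 0.0812, and z = 1.78, giving 96.2%. The other rows give 88.5% and 80.4% (stated: 96%, 89%, 80%). The plan's figures reproduce.

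**2. Effect on the DBS rate.** With true DBS success *p*:

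- ITT rate = p − f·q, because the would-be successes become failures.
- mITT rate = (p − f·q)/(1 − f), because the withdrawn leave numerator and denominator.

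So ITT is unbiased if q = 0, and mITT is unbiased if q = p.

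| f | q | ITT | mITT |
|---|---|---|---|
| 5% | 0.5 | 77.5% | 81.6% |
| 10% | 0 | 80.0% | 88.9% |
| 10% | 0.2 | 78.0% | 86.7% |
| 10% | 0.5 | 75.0% | 83.3% |
| 10% | 0.8 | 72.0% | 80.0% |
| 15% | 0.5 | 72.5% | 85.3% |

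For f = 10% and q = 0.5: 0.80 − 0.10 × 0.5 = 0.75, and 0.75/0.90 = 0.833.

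**3. Effect on ITT power.** Same formula, 100 against 50:

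- f = 10%, q = 0.5 (DBS 0.75). Against control 0.50, z = (0.25 − 1.96 × 0.0817)/0.0829 = 1.085, power 86.1%. Against 0.55, z = (0.20 − 1.96 × 0.0806)/0.0826 = 0.509, power 69.5%.
- Least favourable of the cases taken, q = 0.8, so the DBS ITT rate is 0.80 × (1 − f). Power against control 0.50 and 0.55 is 94.0% and 83.5% at f = 2%, 88.9% and 74.0% at 5%, and 75.5% and 54.6% at 10%. It falls below 80% at f of about 8.6% and 3.2% respectively. Replacing the withdrawn up to 100 evaluable DBS participants restores only 0.1 to 2.4 points.

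**4. No true effect.** True success 0.50 in both arms, exact enumeration of an unadjusted two-sided test. With f = 0 the chance of falsely favouring DBS is 2.8%. With f = 10% and q = 0.2, the DBS rate is 0.480 in ITT and 0.533 in mITT, and that chance is 1.6% and 5.8%. With f = 10% and q = 0.5, ITT is 0.450 and mITT is unbiased.

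**The case against.** Much of the opposing case stands.

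- **Withdrawal is permitted, not required.** Protocol 4.1 also allows extra training sessions, an instructional video and collection by a trained caregiver. Protocol 5.2.1 excludes, before randomisation and in both arms, people who cannot comprehend the website and procedures. That does not test finger-stick skill, but *f* may well be small.
- **The primary analysis errs only one way.** A forced failure in the DBS arm cannot create a false claim for DBS. Treating inability to use the intervention as failure of the strategy is defensible, and the early-withdrawal rule applies to both arms. mITT is supplemental and Completer is for sensitivity only. The answer is that this route to the rule exists in one arm only, and it overwrites tests that the endpoint would otherwise count.
- **Reporting is largely in place.** Reasons for withdrawal go on the CRF and into the CONSORT diagram, and SAP Tables 5 and 6 show terminations and exclusions by arm. That reveals the problem without removing it.

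Three stronger readings are tempting and are not supported.

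- A reader might infer that the maximal-period sensitivity analysis cannot help. SAP 3.3.3 does use the clinician's interval after withdrawal for people who stop DBS collection but allow chart review, and SAP 3.3.5 counts tests to that later date. SAP 4.5.1 does not say whether its pre-discharge failure rule is lifted there. This is an ambiguity.
- A reader might infer that these people drop out of the secondary proportion model in SAP 8.2. SAP 6.5.1 includes them in the ITT analyses but says compliance cannot be calculated and gives a value only for the primary endpoint. The value for the proportion is undefined, and that gap affects early withdrawals in both arms.
- A reader might infer that ITT and mITT are always biased in opposite directions. Step 2 shows that this needs *q* strictly between zero and the overall rate.

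**Conclusion.** The concern holds as a conditional one. A check given after randomisation to one arm is a listed reason for withdrawal. The SAP turns such a withdrawal, if it comes before discharge or the first scheduled test, into a primary ITT failure and an exclusion from mITT and Completer. The ITT effect is against DBS or zero: conservative for superiority, but costly in power. The mITT and Completer effect favours DBS if non-proficient participants would adhere less than others.

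Size rests on *f* and *q*, which the documents do not give. At 10% withdrawn and 50% would-be success, the illustrative gap is 75.0% against 83.3% around a true 80%. If almost nobody fails the check, the effect is negligible. The calculations use unadjusted two-proportion comparisons, not the planned logistic model. The change should be made because it is cheap and removes a difference between the arms that the endpoint does not need.

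**What to change.** 1. **Protocol 5.3.3:** remove proficiency failure as a reason for withdrawal from the study. Record it as *DBS self-collection not started*, keep the participant in quarterly chart follow-up to one year, and do not replace them. Reconcile the mandatory confirmation in Protocol 4.1 with this.
2. **SAP 4.5.1, 6.3.1, 6.5.1 and 8.2:** score these participants' recorded tests in the randomised DBS arm for the primary and secondary adherence endpoints. Reserve the forced failure for those who refuse chart review, and state what value the proportion model uses for them.
3. **SAP 3.3.1:** it now ends adherence follow-up at withdrawal from DBS collection even when chart review is agreed. Amend it so that adherence follow-up continues for these participants.
4. **SAP 6.3.2:** mITT is grouped by intervention received, so anyone without a self-collected sample would move to the control arm. Analyse these participants as randomised.
5. **SAP 3.3.3:** state whether the pre-discharge failure rule applies in the maximal-period analysis.
6. **Reporting:** give the number affected.

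**Cost.** Wording changes in both documents and a little more chart abstraction; Protocol 5.3.3 already keeps sites obtaining CMV disease information after withdrawal. The DBS arm will include some people who never self-collected, which is what ITT intends. Parts of the SAP describe conduct in the past tense, so the protocol change may come too late. The SAP changes could then still be applied to withdrawn participants who agreed to chart review, as far as their test records were obtained.

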5.3.4 Handling of Withdrawals

Eligible subjects who withdraw from the study between randomization and the first scheduled study test (or prior to the start of late CMV surveillance) may be replaced. Reasons for withdrawal will be recorded in the Consort diagram.

6 STUDY INTERVENTION/INVESTIGATIONAL PRODUCT

6.1 Study Product Description

6.1.1 DBS Self-Collection Kit

The HTL Strefa Acti-Lance Safety Lancet (Universal) has been selected as the finger stick device for this trial. This lancet has a quick incision (0.002 seconds) and the 23-gauge needle penetrates 1.8mm, minimizing pain and bruising to the subject. This lancet has a closed design, which ensures that the needle remains inside the lancet before and after the puncture. DBS Self-Collection Kit will be assembled, packaged and distributed to each enrolling site by Fred Hutch (Table 4); the kit will be stored and shipped at room temperature. Each clinical site is responsible for supplying enrolled

Item	Quantity
Lancet	1
Sterile Alcohol Prep Pad	1
Gauze Pad	1
Bandage	1
Whatman 903 Elute Card	1
Subject Label	1
Whatman FTA Multi-Barrier Pouch	1
Desiccant Pack	1
Biohazard Specimen Bag	1
Padded Envelope with Return Address Label	1
DBS Self-Collection Kit Instruction of Use	1

Table 4. Contents of DBS Self-Collection Kit

subjects with collection kits, which includes detailed instruction of use (refer to MOP). Biohazard sharps container will be provided with the initial supply to the subjects for disposal of lancets. Refer to MOP for detailed and updated instructions on study kits and supplies.

6.1.2 CMV PCR

The DBS CMV assay consists of two major steps, an extraction to elute DNA from Whatman 903 Protein Saver Cards and purify it from other blood components on the DBS, followed by a real-time PCR to quantify the CMV present. The CMV PCR assay was initially developed in 2001 using two primer/probe pairs, one of which amplifies the gB region and one the IE region of the CMV genome. Over the last 10 years this PCR assay has been extensively used both clinically and to study CMV infections of immunocompromised patients at both at the University of Washington and the Fred Hutch. This assay has proven to be a valuable tool for detection and monitoring of CMV reactivation and clinical disease.

The DBS testing has been increasingly utilized to detect CMV in studies of congenital CMV by using stored Guthrie cards ^{31–33}. A critical element, which has a significant impact on the assay sensitivity, is the extraction method. A variety of extraction methods have been evaluated in the CAP/CLIA certified University of Washington Molecular Virology Laboratory to identify the method that gives maximum recovery of the virus from the filter paper but elutes the minimum amount of PCR-inhibiting polysaccharides. A study showed good correlation between the levels of CMV in plasma and DBS samples of 35 solid organ transplant patients, using a validated method of Whatman 903 Protein Saver Cards and a chemical extraction with Chelex developed at the University of Washington Molecular Virology Laboratory. The extraction method for the current DBS CMV Testing Device has been modified to use the extraction kit available on the Promega M16 MDx instrument, because of its ability to automate the extraction and to obtain an increased CMV yield.

